4.1.2 Device Specifications

Visica 2™ ICE Probe	
Overall length	8 ft. 6 in. nominal
Shaft Diameter	3.4 mm (0.134 in.)
Shaft Length	13 cm nominal
Shaft Active Freeze Zone	Distal 4.5 cm of Probe Shaft
Shaft Insulation	Proximal portion vacuum insulated

Visica 2™ Console	
Height	60 in. nominal
Width	20 in. nominal
Depth	27 in. nominal
Weight	250 lbs.
Electrical	120 VAC (60 Hz) 6 Amps

4.1.3 Device Operation

The Visica 2™ Treatment System uses a closed system to circulate liquid nitrogen within the probe tip creating sub-freezing temperatures that result in precision cryoablation of the intended target tissue. After the target lesion has been appropriately identified, the Probe is placed under ultrasound guidance into the center of the lesion and cryoablated according to a predetermined freeze algorithm consisting of a freeze cycle followed by a thaw cycle, followed by a final freeze cycle. The probe is then warmed by an internal electrical resistance heater and removed from the patient.

For the purposes of this study, the Visica 2™ Treatment System will be operated in accordance with the Visica 2™ Treatment System Operator's Manual and Visica™ 2 ICE Probes Instructions for Use except for:

- the collection of specific clinical and device operational information and
- the use of a treatment freeze algorithm designed to ablate the target lesion and a margin of tissue, analogous to the surgical margins of a lumpectomy.

4.1.4 Cryoablation Procedure

[figure not shown]
The cryoablation procedure will be performed in accordance with the instructions outlined in the Visica 2™ ICE Probe Instructions for Use except for:

- the collection of specific clinical and device operational information, and
- the use of the treatment freeze algorithm in Table 1.

Representative sonographic images from the cryoablation procedure will be submitted for review by the study radiologist.

[figure not shown]
4.1.5 Probe Positioning Procedure -Locate the target lesion to be ablated using high resolution real-time ultrasound in both the radial and antiradial projections.

- 1) Determine the maximum diameter of the lesion in both projections. Record maximum lesion diameter on the Case Report Form (CRF). *Maximum lesion diameter must be ≤ 2.0 cm and the maximum lesion width dimension must be ≤ 1.5 cm to be eligible for inclusion into the study.*
- 2) Utilizing sterile technique and local anesthesia, a cryoprobe will be inserted percutaneously through a small skin incision (approximately 3-5mm). The probe will be manipulated under real-time ultrasound guidance and the probe tip advanced through the center of the malignant lesion such that the length of the probe shaft penetrates and is centered in the longest imaged lesion plane, as measured above. Proper probe placement will be documented with longitudinal and transverse sonographic imaging.
- 3) Visualize the lesion in the anti-parallel axis relative to probe shaft (i.e., viewed in cross section “end on”). Document probe position within the target lesion with an image printout including:
 - The maximum width dimension shown in that plane. The tumor must measure 1.5 cm or less in the anti-parallel axis relative to the probe shaft. Record this measurement on the CRF.
 - Maximum radius (4b) from the probe shaft to the outermost edge (farthest edge from probe tip) of the target lesion. This measurement should be less than 0.75 cm. Record this measurement on the CRF.
- Print out an image showing both recorded width dimensions above. One or two prints may be produced, but both measurements must show on the print(s).
- 4) Calculate the maximum lesion width dimension to be ablated as 2x the maximum radius as measured above. If the calculated maximum lesion width dimension to be treated (anti-parallel to probe within the target lesion) is greater than 1.5 cm, the probe must be relocated more central to the middle of the lesion.
- 5) Use that calculated lesion width dimension to apply the treatment algorithm in Table I if the calculated maximum lesion width dimension is \geq the largest imaged pre-biopsy lesion width on either mammogram, ultrasound or MRI. If the largest imaged pre-biopsy lesion width on either mammogram, ultrasound or MRI is larger than the calculated lesion width dimension imaged at the time of the cryoablation, use the pre-biopsy lesion width to determine which algorithm should be used.

6) When the probe has been centered adequately, view the lesion in the long axis plane, parallel to the probe shaft and measure the following:

- The maximum lesion dimension shown in that plane. This dimension should not exceed 2.0 cm in the axis parallel to the probe shaft. Record this measurement on the CRF.
- The distance of the probe tip beyond the distal lesion edge. Enter the maximum lesion dimension into the V2 Console. The Console will calculate the distance of the probe tip beyond the lesion (7b) to ensure that the probe is properly positioned.
- Record this measurement on the CRF and print out an image of this measurement.
- Print out an image showing both recorded dimensions above. One or two prints may be produced, but both measurements must show on the print(s).

- 7) Initiate freeze cycles. Treatment Algorithm selected in Table 1. Look at the time listed in the second Freeze cycle in order to confirm that the freeze time is set to either 6 or 8 minutes as referenced in the algorithm.
- 8) Record Treatment Algorithm on the CRF.
- 9) Monitor ice ball growth using ultrasound visualization.
- 10) At the end of HI freeze 1, document maximum ice ball length and width with a printout (including measurements on the print). Record these dimensions on the CRF. Ensure that the ice ball diameter exceeds the calculated maximum lesion width dimension by 10 mm on all sides as determined via ultrasound by extending the HI freeze time if necessary. Record additional HI freeze time and document maximum ice ball length and width with a print out (including measurements on the print) if additional freeze time is required.
- 11) At the end of HI freeze 2, document maximum ice ball length and width with a printout (including measurements on the print). Record these dimensions on the CRF. Ensure that the ice ball diameter exceeds the calculated maximum lesion width dimension by 10 mm on all sides as determined via ultrasound by extending the HI freeze time if necessary. Record additional HI freeze time and document maximum ice ball length and width with a print out (including measurements on the print) if additional freeze time is required.
- 12) After completion of the cryoablation, the probe will be warmed and removed from the breast.

Table 1: Treatment Algorithm		
Max. Width Diameter	< 1.0 cm	1.0-1.5 cm
1st Freeze	HI 6 min US measure and ensure 10 mm margin	HI 8 min US measure and ensure 10 mm margin
THAW	10 min	10 min
2nd Freeze	HI 6 min US measure and ensure 10 mm margin	HI 8 min US measure and ensure 10 mm margin

5 Magnetic Resonance Imaging (Post-cryoablation)

A research breast MRI examination will be performed within 14 to 28 days post-ablation to determine whether any residual tumor can be defined within the targeted lesion.

The cost of the post-ablation MRI will be reimbursed using research funds.

Required Imaging Sequences

- Bilateral pre-contrast axial T1-weighted 3D fast spoiled gradient echo pulse images with fat saturation (≤ 2 mm slice thickness, no gap),
- Bilateral three post-contrast series of axial T1-weighted 3D fast spoiled gradient echo images with fat saturation (≤ 2 mm slice thickness, no gap) with the first post-contrast series obtained immediately after intravenous injection of gadolinium (at T0)
- A delayed sagittal T1-weighted 3D fast spoiled gradient-echo pulse sequence with fat suppression (2-4mm slice thickness, no gap).
- A diffusion-weighted imaging sequence.

A 1.5 Tesla strength or higher magnet and dedicated breast coil should be used.

5.1 Contrast Medium

The intravenous dose gadolinium contrast media should be 0.1 mmol per kilogram of body weight, given via a power injector at a rate of 3 mL/sec, followed by a 20-mL saline flush.

5.2 Review of Ultrasound and MRI Images

The pre-registration and post-cryoablation MRI images of the affected breast and ultrasound images from the cryoablation procedure will be transmitted to the study radiologist after the post-cryoablation visit.

5.2.1 Image Submission

The following materials will be submitted to the study radiologist.

- Pre-registration and post-cryoablation MRI images of the affected breast .
- Ultrasound images from the cryoablation procedure, including images of probe placement parallel and anti-parallel to the probe, and images of the largest dimension of the ice ball at the end of each freeze cycle, representing the ablation zone.
- Copies of corresponding radiology reports.

6.1 Pathology of Surgical Specimen

The surgical resection specimen, following cryoablation, will be oriented by the surgeon in a manner that facilitates the study of all six margins (lateral, medial, anterior, posterior, superior and inferior). The pathologist will ink the specimen margins and serially section the specimen at 2-3 mm intervals in the coronal or sagittal plane (as appropriate for the particular specimen) as is standard for breast specimens at our institution. The entire “cryolesion” will be subjected to histological examination. The remainder of the breast tissue will be thoroughly examined, and histological sections will be obtained from any grossly abnormal areas as well as from random fibrous areas.

Reporting of the histological evaluation of the surgical resection biopsy specimen should be similar to that of the diagnostic core biopsy specimen (See Testing Guidelines section). In addition, the effects of cryoablation (coagulative necrosis, fibrosis, organizing hemorrhage, etc.) will be recorded. The presence of any remaining in situ or invasive carcinoma in the target lesion will be categorized by the pathologist. This study will explore possible methods for quantification and development of an objective scoring system for any residual cancer after cryoablation for breast cancer. Possible methods that may be incorporated or modified include an existing classification model for pathologic assessment of tumor response after neoadjuvant chemotherapy. This includes the Symmans method (J Clin Oncol 2007).

7 Follow-up

7.1 Post-operative Follow-up

Patients will be seen by the surgical team within 14 days after surgical resection. Patients will undergo a physical exam. No further follow-up after the 14-day post-surgery visit will be required for this study.

8 Evaluation of Outcomes

The rate of complete tumor ablation in the target lesion will be evaluated by pathologic review of the surgical specimen.

The negative predictive value of MRI in the post-ablation setting to determine residual in situ or invasive breast carcinoma will be evaluated by radiologic review of pre- and post-ablation MRI imaging.

All patients will be evaluated for adverse events (including pain) associated with cryoablation using history and physical examinations.

The technical variables that may affect success of cryoablation will be reviewed and evaluated in procedure notes and on data forms.

9 Adverse Event (AE) and Serious Adverse Event (SAE) Reporting

The prompt reporting of adverse events is the responsibility of each investigator engaged in clinical research, as required by Federal Regulations.

Toxicities/adverse events must be described and graded using the terminology and grading categories defined in the most current version of the NCI's Common Toxicity Criteria (CTCAE) version 4.0. The CTCAE is available at <http://ctep.cancer.gov/reporting/ctc.html>.

Attribution to protocol treatment for each adverse event must be determined by the investigator and reported on the required forms, using the codes provided.

10 Routine Adverse Event Reporting

All expected or unexpected adverse events, regardless of grade or treatment attribution, must be recorded on AE case report forms (CRFs).

10.1 Expedited AE and SAE reporting definitions

The investigator must initially report the AE within 5 calendar days of learning of the event. If death occurs that is unexpected and definitely, probably or possibly related to study intervention during and within 30 days after the last day of active study intervention, the SAE must be reported within 1 working day (24 hours) from the time the research team becomes aware of the event. All SAEs that do not fall under the prompt reporting requirements will be reported during continuing review using the Internal SAE Log or database printout.

10.2 IRB Policy

We will follow the University of Texas M.D. Anderson Cancer Center IRB policies and procedures in submitting adverse events.

10.3 Expected Adverse Events

Expected AEs from MRI Contrast		
More Likely	Less Likely	Rare but Serious
Heat sensation	Hypotension due to vasodilatation	Hypotensive shock
Dizziness	Mild allergic reaction	Anaphylactic reactions
Nausea	Local pain and tenderness at the injection site	
Headache		

Expected AEs from Cryoablation		
More Likely	Less Likely	Rare but Serious
Pain at site of needle placement	Edema at site of treatment	Hypothermic damage to the skin of the breast
Bruising	Hematoma	Hematoma requiring intervention
Bleeding at site of needle placement	Bleeding requiring suture	Bleeding requiring surgical intervention
Infection	Infection treated with oral antibiotics	Infection requiring IV antibiotics

Expected AEs from Surgical Intervention
Cosmetic deformity from multiple procedures
Treatment delays due to complications

11 Statistical Considerations

11.1 Overview of study design

This is a phase II, one-stage, single arm pilot study to assess the success rate of cryoablation therapy following neoadjuvant chemotherapy in the treatment of invasive breast carcinoma.

11.2 Primary Objective

The primary objective is to determine the rate of complete ablation. Complete ablation is defined as no remaining invasive or in situ carcinoma present upon pathological examination of the targeted lesion. The rate will be computed as the number of patients with complete tumor ablation divided by the total number of eligible patients.

We will declare that the study is feasible if we observe at least 8 patients with complete ablations out of 10 patients.

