1.4 Accrual Goal

A total of 10 eligible and evaluable patients are required for analysis. If results of the pilot study are encouraging and indicate that the study is feasible (see Statistical Considerations, section 12), we will plan a larger study to definitively evaluate the role of cryoablation.

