11.3 Decision rule

There will be three basic decisions made at the end of this trial: recommend the treatment regimen for further trials in selected patient populations, recommend further studies to assess whether modifications to the cryoablation technique can achieve the target goal, or recommend no further studies of this treatment regimen.

If the number of patients with a complete tumor ablation rate is 8 or more (out of 10 eligible patients) we will recommend the treatment regimen for further trials in selected patient populations.

If the number of patients with complete tumor ablation is greater than or equal to 5 but less than 8 (out of 10 eligible patients), we will recommend testing modifications to the cryoablation technique to determine if these will achieve the target goal of 80% success rate or greater.

If the number of patients with a complete tumor ablation rate is less than 5 (out of 10 eligible patients), we will recommend no further studies of this treatment regimen.

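### Sections 1.4 and 11.2–11.3 use different denominators for the primary ablation rate, and nothing says how an aborted procedure or an unassessable specimen counts

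*Combined protocol and SAP*

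**What the plan says.** Three places in the combined protocol and SAP describe the population for the primary rate.

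- Section 1.4 (Accrual Goal): "A total of 10 eligible and evaluable patients are required for analysis".
- Section 11.2 (Primary Objective): "The rate will be computed as the number of patients with complete tumor ablation divided by the total number of eligible patients". The feasibility sentence that follows leaves the patients unqualified: "We will declare that the study is feasible if we observe at least 8 patients with complete ablations out of 10 patients".
- Section 11.3 (Decision rule) attaches each of its three cut-offs to a count "out of 10 eligible patients".

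The endpoint exists only once a specimen has been examined: "Complete ablation is defined as no remaining invasive or in situ carcinoma present upon pathological examination of the targeted lesion" (11.2). The word *evaluable* occurs only in 1.4 and is not defined. The document has no replacement rule. It does not say how to count a patient whose cryoablation is aborted or whose specimen is missing or cannot be assessed, and it gives no cut-offs for a total other than 10.

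**The concern.** The populations agree only if every eligible patient is evaluable. If one is not, 1.4 still asks for ten who are, so at least eleven eligible patients are needed. Section 11.2 then divides by eleven or more, while 11.3 has a rule for ten only. The choice between the sections could be made after the results are known.

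The primary estimate and the trial's only recommend/modify/stop rule depend on that choice. An aborted procedure is unlikely to be independent of whether the technique works. Leaving such patients out would push the rate upward, and Table 2 would no longer describe the rule for eligible patients as a whole.

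**Working it through.** **1. The plan's own figures.** Table 2 uses X ~ Binomial(10, p).

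- P(X ≥ 8) at p = 0.60 = 45(0.6⁸)(0.4²) + 10(0.6⁹)(0.4) + 0.6¹⁰ = 0.1209 + 0.0403 + 0.0060 = 0.167. Table 2 has 0.1683.
- At p = 0.50, 0.70 and 0.80 the exact values are 0.0547, 0.3828 and 0.6778. Table 2 has 0.0525, 0.3816 and 0.6722.
- All 29 entries of Table 2 lie within 0.009 of the exact binomial.
- The exact (Clopper-Pearson) 95% interval for 8/10 is 44.4% to 97.5%, as in section 11.5 and Table 3.

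The tables are therefore sound for a fixed set of 10 patients. What is open is which 10.

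**2. One result, two denominators.** Take 8 complete ablations among 10 evaluable patients, plus k further eligible patients who are not evaluable. The values of k are assumptions; the document gives none.

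| k | Rate under 1.4 | Rate under 11.2 | Exact 95% CI for the 11.2 rate |
|---|---|---|---|
| 0 | 8/10 = 80% | 8/10 = 80% | 44.4–97.5% |
| 1 | 8/10 = 80% | 8/11 = 72.7% | 39.0–94.0% |
| 2 | 8/10 = 80% | 8/12 = 66.7% | 34.9–90.1% |

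With k = 1 or 2 the 11.2 rate is below the "target goal of 80% success rate or greater" in section 11.3, and 11.3 has no cut-off for 11 or 12 patients.

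**3. The decision itself can change.** Let k = 1, and suppose the eleventh patient is one of the 8 successes. The first 10 eligible patients then contain 8 − 1 = 7 successes. Counted over those ten, 7 falls in the band for testing modifications. Counted over the ten evaluable patients, 8 leads to a recommendation for further trials.

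**4. Effect on the chance of a recommendation.** Let p be the true success rate among all eligible patients and d the share not evaluable, with every such patient taken as a non-success. If they are dropped and replaced until 10 are evaluable, the success rate among those analysed is q = p/(1 − d), and the chance of at least 8 is the binomial tail at q. For p = 0.60:

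- d = 5%: q = 0.60/0.95 = 0.632
- d = 10%: q = 0.60/0.90 = 0.667
- d = 20%: q = 0.60/0.80 = 0.750

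| True rate p | All counted | d = 5% | d = 10% | d = 20% |
|---|---|---|---|---|
| 0.50 | 0.055 | 0.076 | 0.106 | 0.211 |
| 0.60 | 0.167 | 0.224 | 0.299 | 0.526 |
| 0.70 | 0.383 | 0.487 | 0.610 | 0.881 |

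The values of d are assumptions, and replacement is an inference from 1.4.

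**5. Who could be non-evaluable.** Sections 1.3 and 4.1.1 plan resection for every patient, and section 6.1 has the whole cryolesion examined histologically. A completed ablation that leaves carcinoma therefore has a pathological result and is a failure on either reading. That leaves aborted procedures and missing or unassessable specimens.

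**The case against.** The best defence is that section 1.4 is an accrual goal and does not define the rate. The only sentence that defines the denominator is in 11.2, and 11.3 agrees with it each time. Read literally, 11.2 keeps an eligible patient without a result in the denominator and out of the numerator, which is already the conservative treatment. This has force, but it does not settle the matter. Section 1.4 says what the analysis requires, and once one eligible patient is not evaluable, the totals in 1.4 and 11.3 cannot both be 10.

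A reader might infer that an evaluable-only analysis removes the patients in whom the technique failed. The documents do not support that: residual tumour after a completed ablation is observed and counted. Nor does the plan say that failures will be excluded or that patients will be replaced; it leaves both open. Some losses, such as a withdrawal, would have nothing to do with the technique.

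A reader might also take section 4.1.5 as a way for technical failures to become ineligible, because step 1 says "the maximum lesion width dimension must be ≤ 1.5 cm to be eligible for inclusion into the study". That step is an ultrasound size check before the probe goes in at step 2, and it repeats the limits of eligibility criterion 4. Step 3 repeats the width limit after insertion without mentioning eligibility. For a poorly centred probe, step 4 calls for repositioning, not exclusion. This sentence does not show that failures are excluded.

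Finally, the stakes are modest. This is a 10-patient pilot in which everyone is resected and a favourable result leads to a larger study. The intervals for 8/10 and 8/12 overlap widely. The ambiguity matters only if some patient is not evaluable and the count is near a cut-off.

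**Conclusion.** The concern holds in this limited form. Two stated populations conflict for the primary rate and for the sole decision rule, and nothing in the document resolves the conflict. One eligible but non-evaluable patient is enough: 8 successes are 80% under 1.4 and 72.7% under 11.2, and 11.3 has no rule for eleven patients. At a true all-eligible rate of 0.60, the chance of at least 8 in 10 rises from 0.167 to 0.224, 0.299 or 0.526 if 5%, 10% or 20% are dropped and replaced.

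Those figures rest on assumed non-evaluable numbers and shares, on replacement as one reading of 1.4, and on every non-evaluable patient being a non-success. They show how far the rule could move and do not predict what will happen. With no aborted procedure and an assessable specimen from every patient, the sections agree.

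**What to change.** Use one denominator in 1.4, 11.2 and 11.3: the first 10 eligible patients in whom cryoablation is started. This fits section 1.2.1, which states the primary objective for patients who received cryoablation.

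- Count a treated patient without a pathological finding of complete ablation as not complete, and do not replace her. This includes an aborted procedure and a missing or unassessable specimen.
- Replace only patients in whom cryoablation is never started, and list them with reasons.
- Delete *evaluable* from 1.4, and report the evaluable-only rate as supportive.

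The cost is a wording change. The number analysed stays at 10, and Tables 2 and 3 stay unchanged. The downside is that the headline rate may be slightly less favourable, and some losses unrelated to the technique will count as failures. The supportive rate and the listed reasons let a reader judge how much that matters.
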